7.10 Discharge, Early Termination, Taper, and Post-study Procedures

Participants withdrawn early from the study will be referred to appropriate services. Participants in the VI and PNV conditions will not require any medication taper.

7.11 Ancillary Medications

Ancillary medications may be provided by the study medical team for study medication-related side effects as clinically indicated. A range of prescription and over-the-counter ancillary medications may be used for anxiety, nausea, vomiting, diarrhea, muscle pain, and insomnia.

7.12 Concomitant Medications

Participants will be instructed to contact the study medical clinician before taking any non-study medications, including prescription drugs, over-the-counter preparations, and herbal supplements, during the course of the study. Participants reporting use of medications that may interact with naltrexone will be excluded or withdrawn based on clinical judgment.

Management of Study Medications

Appropriately qualified and trained medical personnel will maintain an accurate and current accounting of all study medication, which will be available for verification by study monitors. Drug-accountability records including perpetual inventory, will include the amount of study medication ordered, received, transferred between areas of the study site, and those dispensed to individual participants.

7.12.1 Study Medication Storage

Study medication will be stored in compliance with federal, state, and local laws and institutional policy. Study medication will be stored in a locked, secure, limited-access location under the conditions specified by the package insert; Vivitrol will be stored in a locked refrigerator.

7.12.2 Unused Medication

Unused expired study medication will be logged into an inventory of unused medication, and all medications not used by the end of the study intervention phase will be logged and returned to NIDA (or as directed) for destruction. Unused medications will be accurately labeled, securely stored, and kept separately until sent for destruction. Damaged, expired, or unused study medication will be accounted for by the NIDA contract monitor before being returned for destruction. Expired naloxone and other ancillary medications obtained for this study will be destroyed on site or sent for destruction per local institutional policies.

7.12.3 Dispensing of Study Medications

All study medications shall be dispensed by an appropriate licensed physician/nurse practitioner appropriately trained and authorized to dispense study medications. Vivitrol injections will be administered in Week 1, and every four weeks for 24 weeks (total of 6 injections).

7.12.4 Drug Packaging

Vivitrol will be supplied in single use packages. Each package will contain one 380 mg vial of Vivitrol[®] microspheres, one vial containing 4 mL (to deliver 3.4 mL) diluent for the suspension of Vivitrol[®], one 5 mL prepackaged syringe, one 1-inch 20 gauge needle, two 1.5-inch 20 gauge needles, and two 2-inch 20 gauge needles with needle protection devices. Lot number and medication expiration date will be included on the package labels supplied by the manufacturer.

7.13 Participant Withdrawal

There are no formal criteria for investigator withdrawal of a participant, however, any participant for whom study participation is deemed potentially unsafe as determined by the medical clinician will be withdrawn from participation, even if the participant would like to continue. Also, participants who have difficulty complying with the study procedures may be withdrawn.

Participants will be withdrawn from medication if it is clinically determined that continuation may be unsafe. For example, participants who develop uncontrolled hypertension will be discontinued and instructed to see their private physician, or will be provided with referrals for medical care. Women who are assigned to one of the VI conditions and become pregnant during the intervention period will be withdrawn from study medication, referred for medical care, and the pregnancy will be followed until an outcome is known. Participants who experience intolerable side effects or other physical or psychiatric conditions regardless of relationship to the study medication will also be withdrawn from further study medication administration.

The medical clinician may determine that a participant's clinical condition has deteriorated during the course of the study. Examples of clinical deterioration that might trigger a decision to withdraw the participant from medication include the following:

- The initiation or recurrence of risky behaviors that make further participation unsafe;
- Overdose;
- Emergence of psychosis, suicidal ideation, severe cognitive impairment or dangerous criminal behaviors;
- Evidence of general medical deterioration; or
- New onset of psychiatric or medical conditions that would require intervention that would preclude continued participation in the study protocol.

In the event the participant is withdrawn from further medication administration, referrals to treatment programs or recommendations for medical care will be provided. The study medical clinician, in collaboration with the principal investigator may consult with the study medical monitor in making this decision. At any time, participants may decide that they no longer wish to continue to receive medication or to participate in the study. Those who opt out of medication will be allowed to continue to make clinic visits and complete assessments and will complete post-intervention and follow-up assessments.

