2.4 Interventions

All participants will be scheduled for twice-monthly medical management and assessment appointments for the first three months of the 24-week post-release intervention phase, with monthly appointments for months 4-6. Eligible participants will be randomly assigned to treatment condition (VI, PNV, DE) in equal numbers. VI and PNV participants will undergo a naloxone challenge to ensure opioid abstinence at the time of Vivitrol induction. Those in the PNV condition will be provided with a PN who will facilitate attendance at outpatient treatment programs as well as assist with other needs. The DE group will not receive any medication but will be scheduled for assessments and education on drugs of abuse, maintaining abstinence, and methods for avoiding overdoses on the same schedule as the other two groups. The DE group will also be

provided with naloxone kits to be used in the event of overdose. All groups will also be provided with referrals to community-based substance abuse treatment programs.

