7.3 Random Assignment

Eligible participants will be randomly assigned to study condition (VI, PNV, DE) in a 1:1:1 strategy using an urn randomization procedure (Stout et al., 1994) to provide multivariate balance across two characteristics correlated with outcomes in addiction treatment trials: type of opioid (heroin or prescription drug) and gender.

Individuals who terminate participation before induction onto the assigned medication (or similar time-point for behavioral assignments) will be replaced. Those terminating after VI induction or provision of the first DE session will not be replaced and will be counted as "treatment failures" (in an intent-to-treat scenario).

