10.0 STATISTICAL ANALYSES

The project emphasizes evaluation of the clinical utility of Vivitrol in jail inmates as compared with a Drug Education condition (DE), while descriptive statistics will provide an overall assessment of the implementation of the protocol.

Analyses will include an Intent-to-treat (ITT) design such that all randomized participants who received at least one dose of medication (VI, PNV), or received at least one session of drug education (DE) will be included who did not violate the protocol in a way that could potentially affect the efficacy results. Participants will be excluded from the Protocol Population (PP) if:

- 1. concomitant medication that is known to have significant clinical effect on primary or secondary endpoints was administered.
- 2. Violations of the inclusion or exclusion criteria are judged to affect the efficacy evaluations.

Subjects in the PP population will be allocated to treatment groups in the analysis based on the actual treatment they received. If there is substantial difference between the ITT population and the PP population, all analyses described below will be performed using only subjects in this group.

All statistical tests will be performed using two-sided .05 significance levels, unless otherwise stated. All comparisons between treatments will be reported with parameter estimates and 95% confidence intervals. For parameters measured at baseline and subsequently, the variables of interest are changes from baseline.

Post-baseline variables will not be imputed; estimates can be obtained using the hierarchical models specified below under the assumption of missing at random. For the primary outcome measure, diagnosis at six months, subjects who have dropped out for whatever reason will be considered to retain the diagnosis. Other outcome measures for which data are missing will be imputed using multiple imputation methods. Sensitivity analyses will repeat specific analyses using permutation tests of at least 1000 samples.

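### Staff may withdraw participants from the trial with no month-6 assessment stated for them, while dropouts for any reason are scored as still having the diagnosis

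*Combined protocol and SAP*

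**What the plan says.** **Withdrawal by staff.** Section 7.13 states that there are no formal criteria. A person for whom participation is judged potentially unsafe "will be withdrawn from participation, even if the participant would like to continue". It adds that "participants who have difficulty complying with the study procedures may be withdrawn", without saying from what. A separate paragraph of 7.13 deals with withdrawal from medication.

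**Assessment afterwards.** Section 7.13 ends: "Those who opt out of medication will be allowed to continue to make clinic visits and complete assessments", including post-intervention and follow-up assessments. Section 7.10 says "Participants withdrawn early from the study will be referred to appropriate services" and mentions no assessment. Appendix A (Participant Withdrawal) asks for an end-of-medication visit, but only when withdrawal is voluntary. For the control arm, abstract section 2.4 (Interventions) says "The DE group will not receive any medication but will be scheduled for assessments".

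**Scoring.** For the month-6 diagnosis, section 10.0 says "subjects who have dropped out for whatever reason will be considered to retain the diagnosis". Section 7.3 says "Those terminating after VI induction or provision of the first DE session will not be replaced and will be counted as" treatment failures.

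**Scope of withdrawal.** Section 7.13 and Appendix A treat pregnancy and most adverse events as reasons to stop medication. The abstract (2.3 Assessments) says that a safety-compromising adverse event ends participation, section 5.3.2 says that a pregnant participant leaves the study, and section 7.12 says only that some people are withdrawn.

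**The concern.** Stopping treatment and stopping outcome assessment are different acts, and the plan does not keep them apart when staff make the decision. Someone withdrawn for safety or poor compliance may be willing and able to give a month-6 interview. No section says that the interview is attempted, and the scoring rule then supplies a failure.

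Section 7.14 makes the trial open-label, so staff know the arm when they use this discretion. Medication side effects arise only in the VI arm and the arm given Vivitrol with a patient navigator (PNV), while compliance problems can arise in any arm. Unequal withdrawal is therefore possible, and each withdrawn person without the disorder adds a false failure to one of the two primary outcomes. The only sensitivity analysis named in section 10.0, permutation tests, leaves the scoring as it is.

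**Working it through.** **Step 1: who is promised an assessment.**
- Opts out of medication: yes (7.13).
- Withdraws voluntarily from treatment because of an adverse event or another reason: an end-of-medication visit (Appendix A), which is not a month-6 assessment.
- Withdrawn by staff from medication only: not named, since this person did not opt out.
- Withdrawn by staff from participation: none stated, only referral (7.10).
- DE participant withdrawn by staff: none stated; with no medication to opt out of, the promise in 7.13 cannot apply literally.

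**Step 2: the plan's own figures.** Section 10.3 gives 150 randomized, 50 per arm, and 10-20% dropout. 150 × (1 − 0.20) = 120, the stated evaluable number; 10% dropout would give 135. The plan gives no rate of staff withdrawal by arm and no expected diagnosis rate.

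**Step 3: shift in the VI versus DE difference.** Let k be the net imbalance between the arms in people withdrawn by staff and not assessed. Let q be the share of them who truly have the disorder, taken as equal in both arms. Scoring all of them as diagnosed adds k(1 − q) false diagnoses, so

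shift = (k/50) × (1 − q).

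Both k and q are assumptions. Results in percentage points:

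| k | q = 50% | q = 70% | q = 90% |
|---|---|---|---|
| 1 | 1.0 | 0.6 | 0.2 |
| 2 | 2.0 | 1.2 | 0.4 |
| 3 | 3.0 | 1.8 | 0.6 |

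**Step 4: scale against sampling error.** At assumed true rates of 40% and 60%, the standard error of the difference is √(2 × 0.24/50) = 0.098.
- k = 1, q = 50%: 0.010/0.098 = 0.10 standard errors.
- k = 3, q = 50%: 0.030/0.098 = 0.31.
- k = 3, q = 40%: 0.036/0.098 = 0.37.
- k = 3, q = 0: 0.060/0.098 = 0.61.

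**Step 5: the handling rule matters too.** Section 10.0 also limits the analysis set to people "who did not violate the protocol in a way that could potentially affect the efficacy results". Take an arm with 20 of 50 diagnosed, in which one person without the disorder is withdrawn. The arm's rate is 20/50 = 40.0% if that person is assessed, 21/50 = 42.0% if imputed as a failure, and 20/49 = 40.8% if excluded.

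**The case against.** The strongest reply is that the affected group may be nearly empty. Section 7.13 sends almost every concrete trigger to withdrawal from medication: unsafe continuation, pregnancy, intolerable side effects, overdose, psychosis, suicidal ideation and general deterioration. Two of these triggers are themselves worded as problems with participation, so the opening sentence need not mean loss of assessment. The scoring rule sits among the missing-data rules, and nothing there overrides a diagnosis that was obtained. Scoring dropouts as failures is prespecified and applies to all arms, and section 10.3 describes the trial as preliminary.

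Much of this stands. It limits the likely number affected and the size of the problem. It does not supply the missing statement: no section provides for a month-6 assessment after staff withdraw someone from participation, or for a withdrawn DE participant.

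A reader might infer more than the text supports:
- **That every safety or pregnancy withdrawal loses its outcome.** Section 7.13 and Appendix A make most of these medication-only.
- **That the plan forbids a month-6 assessment.** It is silent.
- **That opioid use is scored the same way.** Section 7.3 does not limit its treatment-failure label to one outcome, but section 10.0 sends missing data on outcomes other than the diagnosis to multiple imputation.
- **That the bias is large.** With true rates of 40-60%, a spurious 2 to 12 points needs 5-20% extra staff withdrawal in one arm (0.05 × 0.40 = 0.02; 0.20 × 0.60 = 0.12). The plan expects 10-20% dropout of all kinds.

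**Conclusion.** The gap is real and worth closing, but it does not threaten the trial. Under the stated rules an unblinded staff decision can turn an assessable participant into an imputed failure on the month-6 diagnosis. For a net imbalance of 1 to 3 people and q of 50-90%, the VI versus DE difference moves by 0.2 to 3.0 points, up to 0.31 standard errors. This is not a ceiling: with k = 3 it reaches 0.37 at q = 40% and 0.61 at q = 0.

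A reader might infer that the rule works against medication. The documents do not support a direction, because they give no withdrawal rates by arm or type.

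The figures rest on assumed k, q and diagnosis rates, and on the retain-diagnosis rule being the one that governs. It is the rule written for this outcome, although section 10.4.2 also assumes missing at random. The primary contrast in 10.4.2 pools data from other sites whose numbers are not given, so the shift there is unknown.

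**What to change.** In section 7.13, state that:
- withdrawal by the investigator, in any arm, is from study treatment only;
- the month-6 outcome assessment and the planned follow-up are still attempted for everyone who received a first injection or first DE session, unless consent is withdrawn or the assessment itself is unsafe.

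In section 10.0, state that missing counts as diagnosed only when the month-6 diagnosis is not obtained. Align the abstract (2.3 Assessments), section 5.3.2 and section 7.12 with the medication-only wording in 7.13 and Appendix A. Report withdrawals by type (treatment or assessment), reason and arm.

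The rules for stopping treatment and for replacing people who leave before induction do not change. The cost is some protocol wording, one field on the withdrawal form, and continued contact with a few participants at visits already planned. The exception for an unsafe assessment still rests on clinical judgment, but on a narrower question, and the reported reasons would show how often it is used.

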7.14 Blinding

This is an open-label, non-blinded trial.

7.15 Participant Reimbursement

Study participants will receive gift cards or cash as compensation for time, travel, parking, and other costs borne by the participant. Participants will be provided with medical management at no cost, and those in the VI and PNV conditions will receive no-cost medication.

Incentives will be provided for participating in screening, twice-monthly medical management visits in months 1-3 and monthly visits in months 4-6 during the intervention phase, and assessment visits at months 1, 3, 6, and 12. A \$25 incentive will be provided for screening; \$20 for each of 9 medical management visits (\$180), \$40 for each of 3 post-release assessment visits (\$120), and \$80 for a final visit at month 12. Each participant will be eligible to receive \$405.

8.0 STUDY ASSESSMENTS

Measures and instruments will be used to ensure a comprehensive assessment of status and functioning variables. These data, along with the DATCAP, will also be used to support the economic analysis. (The DATCAP will be administered during Year 2.) On average, screening and eligibility assessments will be completed in 4-6 hours (specific to treatment group). Post-release assessments will be completed in approximately 30-60 minutes. Medication Management visits are expected to take approximately 30-60 minutes.

Timepoints	Screening	Pre-	Post-release	
_		release		
Clinic Visits			Medical Mgmt	Assessments
				Months 1, 3,
				6, 7, 12
Measures				
Safety & Med. Measures				
Physical Exam / Med History	Х			
Injection site inspection	Х		X	
Vitals	Х		X	
12-lead ECG	Х			
Clinical Lab Tests	Х			
HIV Test	Х			
Pregnancy Test	Х		X	
Prior/Concomitant Meds	Х		X	
AEs			X	Х
Drug Use Measures				
DSM-5 Checklist	Х			
COWS (Withdrawal)	Х			
SOWS (Withdrawal)	Х			
Urine Drug Screen (UDS)	Х	Х	X	Х
Substance Use Report (TLFB)	Х	Х	X	Х
VAS (Craving)	Х	X	X	X
Crime and Recidivism				
Self-Report Arrest/Tx History			X	Х
Arrest Records				Х
CJ-DATS Crime Grid	Х			
HIV Risk Measure				
HIV-GAIN	Х			X
Cost				
Form 90				

Table	1. Data	Collection	Time and	Event	Schedule
I UDIC	I. Dutu	00110011011	This and		ouncaute

8.1 Safety and Medical Measures

8.1.1 Medical and Psychiatric History

The participants' medical and psychiatric history will document past and present health conditions at screening to help determine eligibility and to provide baseline information.

8.1.2 Physical Examination

A physical examination will be completed at screening to ensure that there are no exclusionary medical conditions and to gather baseline information. An examination of the participant's body habitus will address appropriateness for VI gluteal intramuscular injection.

8.1.3 Injection Site Examination

Appropriate medical personnel will examine the injection site on the visit following each injection procedures. Additional monitoring may be required. Participants will be asked to immediately report any site reactions to allow evaluation, monitoring, and possible referral, as needed. Injection site examinations will be documented.

8.1.4 Electrocardiogram (ECG)

A 12-lead ECG will be administered at screening.

8.1.5 Clinical Laboratory Tests

A comprehensive blood chemistry including liver function, hematology panel, and a standard urinalysis will help determine eligibility at screening. An accredited laboratory (College of American Pathologists or equivalent), that meets CLIA guidelines, will provide lab results, normal values, and proof of lab certifications.

8.1.6 HIV Testing

On-site HIV testing will use the FDA-rapid test (INSTI™ HIV-1 Antibody Test Kit; bioLytical Labs, Inc.), providing results within one minute to ensure participant awareness of HIV status.

8.1.7 Pregnancy and Birth Control Assessment

Pregnancy test information will be collected for female participants and include test results, and self-reports of birth control method(s).

8.1.8 Vital Signs

Vital signs (e.g., body temperature, blood pressure, pulse, respiration rate) will be collected at screening, at each medical management visit throughout the intervention phase, before and after naloxone administration, at Vivitrol injections.

8.1.6 **Prior and Concomitant Medications**

Information about prescription, over-the-counter medications, and herbal supplements used by participants will be collected at screening for medications taken in the previous 4-week period. At other medical management visits, the form will document medications taken since the previous data collection visit.

8.1.7 Adverse Events (AEs) and Serious Adverse Events (SAEs)

Medical or psychiatric adverse events (AEs) will be collected by inquiring of participants: "How have you been feeling since your last visit?" AEs will be recorded at each visit after consent according to the adverse event reporting definitions and procedures. If a reported AE suggests medical or psychological deterioration, it will be brought to the attention of the study medical clinician for further evaluation, and seizures will also be reported to the DSMB as they occur. SAEs will be medically managed, reported, and followed in accordance with applicable regulatory requirements.

8.2 Drug Use Measures and Psychological Measures

8.2.1 Substance Use Report: Timeline Follow-Back (TLFB)

The TLFB will be used to elicit participants' self-reported use of alcohol and illicit substances. At screening, substance use reported by the participant for the prior 30-day period will be assessed. The TLFB will be administered at each study visit throughout the medication phase, at the post-medication visit, and at follow-up to document the participant's self-reported use of substances for each day since the previous assessment.

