5.3 Study Population

Participants will be 150 individuals meeting DSM-5 criteria for opioid use disorders who are 18 years and older, have been detoxified from opioids in the Bernalillo County Metropolitan Detention Center and meet eligibility criteria.

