5.3.1 Inclusion Criteria

Study participants *must*:

- 1. Be at least 18 years of age or older,
- 2. Meet criteria for DSM-5 opioid use disorders,
- 3. Be detained for at least 48 hours,
- 4. Have an expected release date within one year,
- 5. Plan to reside in area after release,
- 6. Have at least one instance of relapse to opioid use after a period of abstinence.

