5.4 Participant Recruitment

Recruitment through a close collaboration with the Bernalillo County Metropolitan Detention Center (BCMDC) staff, combined with IRB-approved presentations and posted announcements in the jail facilities will proceed until 150 participants are recruited, consented, and randomized. Given the potential recruitment pool of more than 80 individuals per month, it is expected that an average of 6-8 individuals will be randomized per month across the 20-month enrollment period. Based on prior evidence in similar trials, refusals and early (pre-randomization) dropouts will account for approximately 20% of individuals presenting for screening.

Recruitment plans include hypervigilence to the issue of voluntariness. All BCMDC and study staff will be extensively trained on this issue to ensure that their actions and words do not convey any level of coercion. Training will include a discussion of the fact that treatment and study compliance are optimized when participants have the opportunity to consider the study, ask questions, and provide voluntary consent to participate. Furthermore, all recruitment documents and the ICF will emphasize that decisions whether or not to participate are solely up to the individuals, that the decision will not affect the treatment or possible treatment to which the individual is eligible, that participation/non-participation will not affect the sentence, release, probation, or any other aspect of the individual's incarceration.

The main method of recruitment will be announcements of the study made to inmates in the Bernalillo County Metropolitan Detention Center (BCMDC). An informational flyer will be provided to arrestees who are within 4 weeks of release and have been detoxified from opioid use. Individuals who convey interest in this study to jail staff will be referred to study staff. If still interested after receiving a description of this study, study candidates will complete a consent process that includes an detailed explanation of the study, risks and benefits, and that study

participation is voluntary and will have no effect on a participant's sentence, jail term, probation, parole, or release.

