5.5 Study Sites

UCLA Integrated Substance Abuse Program (ISAP). The leadership, data management, and analysis portions of the proposed project will occur at UCLA ISAP in Los Angeles.

[name], will be the physician PI for this study. He has extensive experience in both the use of Vivitrol and behavioral treatments. He will be involved in supervision of the medical aspects of this study, randomization, and will meet regularly with other study personnel. He has conducted over a dozen clinical trials using MAT and will be responsible for medical team training. More recently, he has conducted research using Vivitrol and has been instrumental in the training of other ISAP medical personnel on the Vivitrol injection.

For this project, the primary sites for recruitment, data collection, and treatment services are the Bernalillo County Metropolitan Detention Center and the University of New Mexico, Department of Psychiatry.

Bernalillo County Metropolitan Detention Center (BCMDC). Recruitment and induction will occur at the jail sites in the BCMDC System. The jail facility houses sentenced and unsentenced inmates. The types of inmates housed here are general population, violent/assaultive offenders, psychiatric, and inmates needing medical services. This facility is staffed with Sheriff Service Technicians, intake and release specialists, medical service staff contracted by the County Behavioral Health Department, and clerical support staff. Bernalillo County opened the MDC facility in 2003. Currently, the MDC averages about 40,000 bookings per year, with an average daily population of 2,636. Males account for 87% of the inmate population. With regard to race/ethnicity, 54% are Hispanic, 23% White-Non-Hispanic, 12% American Indian, 9% African-American, 0.4% Asian, and 1.7% are categorized as "Other." Currently the MDC detoxifies an average of 758 individuals monthly—412 from alcohol and 346 from opiates.

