7.4 Medication Pre-Induction

7.4.1 Vivitrol Pre-Induction

Vivitrol Pre-administration and Injection Procedures. Individuals must be free from opioids for at least 7 days before receiving the Vivitrol injection, which is confirmed via self-report and facility records. To ensure opioid abstinence at time of induction, a naloxone challenge will occur followed by one day of oral naltrexone before Vivitrol injection, adhering to NIDA-approved and IRB-approved procedures. Subsequent Vivitrol injections administered every four weeks will require confirmation of opioid abstinence by either naloxone challenge or administration of oral naltrexone, as determined appropriate and necessary by the Study Physician and/or Nurse Practitioner (NOTE: In New Mexico, a Nurse Practitioner [NP] has virtually all the same medical privileges as a Physician and can function as an Physician).

The pre-induction strategy includes:

- *Step 1.* Participants must self-report no clinically significant opioid use (i.e., at any level that could constitute a potential risk of precipitating opioid withdrawal upon naloxone administration in the next step) in the previous seven days.
- *Step 2.* A urine drug screen will be administered shortly before the naloxone challenge and must be negative for opioids. Individuals who are opioid-negative will continue in the pre-induction process. Individuals may have an additional urine drug screen on a subsequent day if the study medical clinician determines that a second screen is appropriate.
- *Step 3.* Completion of all pertinent psychosocial and medical screening and eligibility assessments.

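### The baseline TLFB covers the 30 days before an in-jail screening, so baseline opioid days mix custody and community time and change from baseline is not change in community use

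*Combined protocol and SAP*

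**What the plan says.** Section 8.2.1 (TLFB): "At screening, substance use reported by the participant for the prior 30-day period will be assessed". Later administrations cover each day since the previous assessment.

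Screening is done in custody. Section 5.5 states: "Recruitment and induction will occur at the jail sites in the BCMDC System". The recruitment flyer in section 5.4 goes to "arrestees who are within 4 weeks of release and have been detoxified from opioid use", and section 7.2 has staff confirm completed detoxification with the jail before the consent and screening appointment.

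Time already served at screening has a floor but no ceiling. Section 5.3.1 requires participants to "Be detained for at least 48 hours". The companion criterion, "Have an expected release date within one year", limits the time still to serve, not the time served. Section 4.1.1 describes jail stays as ranging from days to months.

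On the use of the baseline, section 10.0 says that for anything measured at baseline and later "the variables of interest are changes from baseline". Section 2.4 (Analyses), however, defines the opioid-use outcome as the number of use days in the 30 days before the month-6 assessment, which is a level. Sections 2.4 and 10.4.3 set costs against changes in effectiveness measures, and 10.4.3 gives days of abstinence as an example.

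**The concern.** The two 30-day counts look alike but describe different settings. The month-6 count is meant to describe life after release. The baseline count describes whatever part of the previous 30 days was spent outside, plus the days spent inside. Two people with the same community habit can have very different baselines only because one was held longer.

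The pre-release TLFB in Table 1 does not help. Under section 8.2.1 it runs from the previous assessment, so it too covers custody. The plan thus contains no TLFB count of a full community month before treatment.

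If the change rule in section 10.0 is followed, a participant who leaves jail and resumes exactly the earlier pattern is scored as worse, by an amount set by days in detention. Statements about change within an arm, and economic results that use an arm's own change, inherit this artefact. Between-arm contrasts of change inherit extra variance.

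**Working it through.** **1. Custody share of the window.** Share = min(days held, 30)/30. The 48-hour minimum is from section 5.3.1; the other durations are illustrations. The last two columns assume no use in custody, use on 90% of community days, and an unchanged habit over a full community month at month 6 (0.9 × 30 = 27 days).

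| Days held at screening | Custody share | Community days | Baseline use days (0.9 × community days) | Apparent change to 27 |
|---|---|---|---|---|
| 2 | 2/30 = 7% | 28 | 25.2 | +1.8 |
| 7 | 7/30 = 23% | 23 | 20.7 | +6.3 |
| 14 | 14/30 = 47% | 16 | 14.4 | +12.6 |
| 30 or more | 100% | 0 | 0 | +27 |

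True change is zero in every row. Custody takes more than half of the window only after more than 15 days held.

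**2. What the documents imply about days held.** They do not give this for participants. Section 5.5 reports about 40,000 bookings a year and an average daily population of 2,636, so the mean stay is 2,636 × 365 / 40,000 = 24.1 days over all bookings. If days held at screening were exponential with that mean, given at least 2 days (an assumption), expected custody in the window is 2 + 24.05 × (1 − exp(−28/24.05)) = 18.5 days, or 62%. This shows that a majority share is plausible, not that it occurs.

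**3. Power of a change score.** The plan gives no power figure for a change score. Section 10.3 states 120 evaluable, hence 40 per arm, with about .70 power for an effect of .60 and .80 for .5. A two-sided .05 t-test of 40 v 40 gives .755 and .598, so those figures are not reproduced. That is a separate matter, and .598 is used here only as the reference.

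Set the month-6 SD to 1, the baseline SD to k and their correlation to rho. The change-score SD is sqrt(1 + k² − 2·rho·k), and the effective size is .5 divided by it. Both k and rho are assumed.

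| Analysis, 40 v 40, d = .5 | SD | Effective size | Power |
|---|---|---|---|
| Month-6 days alone | 1 | .500 | .598 |
| Change, rho = 0, k = 1 | 1.414 | .354 | .345 |
| Change, rho = 0, k = .5 | 1.118 | .447 | .506 |
| Change, rho = 0, k = .25 | 1.031 | .485 | .572 |
| Change, rho = .2, k = 1 | 1.265 | .395 | .415 |
| Change, rho = .2, k = .5 | 1.025 | .488 | .577 |

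The change score loses power whenever k exceeds 2·rho. An uninformative baseline used as a covariate (rho = 0) leaves power essentially at the month-6 value, since the residual SD sqrt(1 − rho²) stays at 1.

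**The case against.** The strongest reply is that the primary comparison does not need this baseline. Section 2.4 defines opioid use as a month-6 level, and the other primary outcome is a month-6 diagnosis. Time held before screening precedes randomisation, so it is balanced across arms in expectation, and the apparent worsening on release cancels between arms. All of this stands. A reader might infer that the artefact biases the treatment comparison; the documents do not support that.

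A reader might also infer that the baseline is mostly custody time. That is not shown. The entry floor permits a 7% share, and the 24-day mean covers all bookings rather than participants. Nor does the rule "Individuals must be free from opioids for at least 7 days before receiving the Vivitrol injection" establish it, because that rule applies before injection and not at the screening interview. Zero use in custody is itself an assumption, as section 4.1.1 mentions reports of drugs being available in jails.

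The power figure of .35 should not be quoted alone. It needs equal SDs and zero correlation. If long detention pushes baselines towards zero, their spread shrinks and the loss shrinks with it.

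Finally, section 10.4.2 does not name baseline opioid days as a covariate, and a weak covariate does little harm. That is also right. What remains is that the general rule in section 10.0 literally covers TLFB days, and no passage exempts them.

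**Conclusion.** The point holds in limited form. Following sections 8.2.1 and 10.0 as written gives a baseline whose meaning depends on how long each participant has been held, and changes from it that cannot be read as change in community use.

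The harm falls on change scores, statements of change within an arm, and cost-effectiveness results built on changes. In an incremental ratio between arms the shift cancels in expectation and leaves noise; in a figure based on one arm's own change it does not cancel. The baseline is also of little value as a covariate.

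Under the stated assumptions (40 per arm, d = .5, rho = 0), power falls from .60 to between .35 (baseline SD equal to the month-6 SD) and .57 (one quarter of it). The custody shares are plain arithmetic; their distribution among participants is unknown.

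**What to change.** In section 8.2.1, define the baseline TLFB as the last 30 days in the community before the current incarceration, and record the number of days in custody at screening. The existing window can be kept as a description of recent use.

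In section 10.0, state that month-6 opioid days are compared directly between arms, with the new baseline as a covariate and not as a change score. In section 10.4.3, say which baseline any change in drug use refers to.

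The cost is one changed recall window and one added item. The real downside is longer and less accurate recall for people held for months, with error that also grows with time held. The recorded custody days allow this to be examined.
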